### Adverse Event Reporting

Our patient population is by definition critically ill in the ICU. It is expected that they will have a number of unrelated adverse health events (AE) during the course of their hospital stay. Therefore, we will limit the scope of our AE monitoring and recording to the following:

- Serious Adverse Events, defined as
  - Death, believed to be related to the study drug, or a death that is unexpected considering the acuity of a patient
  - A life-threatening experience believed to be related to the study drug
  - Persistent or significant disability or incapacity that is of greater frequency or severity than what would be normally expected in the course of critical illness
  - An event that jeopardises the Human Subject and may require medical or surgical treatment to prevent one of the preceding outcomes and is not expected in the course of critical illness
- Adverse Events possibly related to the study procedures are pre-specified in the list below:
  - Hypertension
  - Bradycardia
  - Hemodynamically significant tachyarrhythmia
  - New organ failure

Evidence for adverse events related to midodrine will be assessed until completion of all study measurements. They will also be included in the FDA Annual Progress Report.

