### **POSSIBLE BENEFITS**

We cannot guarantee any personal benefits from participating in this study. However, potential benefits to the subject may include shorter duration of receiving IV vasopressors, and shorter length of stay in the ICU and hospital. Earlier discharge from the ICU and hospital reduces the risk of developing nosocomial infections and reduces the total cost of the hospital admission. Information gathered from this study will help researchers determine if midodrine is safe and effective at decreasing duration of IV vasopressors and shortening ICU length of stay without increasing the risk of ICU readmission or increasing hospital length of stay.

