### **POSSIBLE RISKS AND ANALYSIS OF RISK/BENEFIT RATIO**

The very common side effects of midodrine reported in previous studies include pilomotor-like reactions, paraesthesia, pruritus, and dysuria. The most common side effects are headache, supine hypertension, flushing, rash, nausea, dyspepsia, stomatitis, chills, and pain. Less common side effects comprise sleep disorders, insomnia, restlessness, excitability, irritability, and reflex bradycardia. Rare side effects are tachycardia, palpitations, abnormal hepatic function, raised liver enzymes.

These reactions rarely resulted in discontinuation of medication. These side effects may make the subject uncomfortable but do not pose any immediate harm. The subject will be assessed daily by study personnel and all efforts will be made to minimise discomfort from these side effects. Other risks that the subject may be exposed to

as a result of midodrine include hypertension, bradycardia, and tachyarrhythmias.

Patients enrolled in the study will have the same safeguards as non-study patients in an ICU setting. For patients who have stable blood pressure and adequate tissue perfusion, midodrine has been used off-label frequently to treat hypotension in our ICU. Therefore, the risks and benefits of the study drug are similar to the risks and benefits of the current standard for treating this indication in ICU patients.

Midodrine is a pregnancy category C medication. Pregnant subjects will be excluded from the study because the exposure risks of midodrine to a developing fetus are unknown. Women between the ages of 18–55, who have not had a surgical hysterectomy, will only be eligible for inclusion if they have a negative urine pregnancy test. Pregnancy testing will not need to be repeated if there is a documented negative urine pregnancy test that was obtained within 7 days prior to starting study drug, provided the woman was an ICU inpatient throughout that period of time.

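### Adverse-event recording leaves out midodrine's very common reactions, so the trial can compare haemodynamic safety by arm but cannot describe tolerability

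*Combined protocol and SAP*

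**What the plan says.** The protocol's Adverse Event Reporting section notes that critically ill patients have many unrelated events and then sets a limit: "Therefore, we will limit the scope of our AE monitoring and recording to the following". Two groups follow. The first is serious adverse events, each qualified by relatedness, unexpectedness or excess over what critical illness would produce. The second is introduced by "Adverse Events possibly related to the study procedures are pre-specified in the list below" and holds four items: hypertension, bradycardia, haemodynamically significant tachyarrhythmia and new organ failure.

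The section on possible risks describes the drug's known reactions: "The very common side effects of midodrine reported in previous studies include pilomotor-like reactions, paraesthesia, pruritus, and dysuria". It says of the side effects it lists: "These side effects may make the subject uncomfortable but do not pose any immediate harm". It also commits to follow-up: "The subject will be assessed daily by study personnel and all efforts will be made to minimise discomfort from these side effects". Separately, it names further risks "as a result of midodrine include hypertension, bradycardia, and tachyarrhythmias".

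Under Possible Benefits the protocol says: "Information gathered from this study will help researchers determine if midodrine is safe and effective at decreasing duration of IV vasopressors". The sentence goes on to ICU stay, ICU readmission and hospital stay.

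The SAP section on primary and secondary outcomes compares the incidence of adverse events between arms with a chi-square or Fisher's exact test.

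**The concern.** The stated reason for the limit is the high background of unrelated illness in the ICU. That is a good argument against open-ended collection. It is a weaker argument against a short solicited list of known drug reactions in a blinded, placebo-controlled trial, where the placebo arm measures the background.

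The two sections also do not fit together. One has study personnel assess patients daily in the context of these side effects. The other keeps the non-serious findings out of both monitoring and recording.

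At stake is how the safety results can be read. The SAP comparison and the data safety monitoring board's review can use only what was recorded, so a safety table without urinary, skin or mild hepatic reactions would say nothing about whether they occurred. The background section already infers good tolerability at one centre from the absence of submitted safety reports, and it acknowledges that safety data for off-label use are limited. A randomised trial is the chance to replace that inference with counts by arm.

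**Working it through.** **Step 1. Set the lists side by side.**

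| Effect | Where the protocol names it | On the recorded list? |
|---|---|---|
| Pilomotor-like reactions | Risks: very common | No |
| Paraesthesia | Risks: very common | No |
| Pruritus | Risks: very common | No |
| Dysuria | Risks: very common | No |
| Urinary retention | Exclusion criterion (acute) | No |
| Raised liver enzymes | Risks: rare | Only if they amount to new organ failure |
| Hypertension, bradycardia, tachyarrhythmia | Risks: further risks | Yes, all three (tachyarrhythmia if haemodynamically significant) |

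Of the very common reactions, 0 of 4 are recorded unless serious. Of the separately named haemodynamic risks, 3 of 3 are recorded.

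**Step 2. Look for another section that restores them.**
- Outcomes, in both protocol and SAP: the safety endpoints are the three haemodynamic events only.
- Study Procedures and SAP Data Collection: liver tests are collected at enrolment or baseline. The items recorded during the study include daily SOFA, blood pressure goals and drug times, but no symptoms, urinary events or repeat liver enzymes.
- The close of Adverse Event Reporting says evidence for midodrine-related events will be assessed until measurements are complete. That sets a period and adds no event types.

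Nothing restores them.

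**Step 3. How many cases could go unrecorded.** The plan gives no reaction rates, so there is no figure of its own to reproduce. Rates of 5% and 10% are assumed for illustration. Arm size is 120/2 = 60 at the target, or 50 as in the SAP's power statement. Because the analysis set is everyone dosed at least once, the true number should lie nearer 60.

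P(at least one case) = 1 − (1 − p)^n; expected cases = n × p.

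| Assumed rate | n = 60 | n = 50 |
|---|---|---|
| 10% | 1 − 0.90^60 = 99.8%; 6 expected | 1 − 0.90^50 = 99.5%; 5 expected |
| 5% | 1 − 0.95^60 = 95.4%; 3 expected | 1 − 0.95^50 = 92.3%; 2.5 expected |

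Under the limit as written, the recorded count for non-serious cases is zero whatever the true rate.

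**Step 4. What recording would allow.** Normal-approximation power for two proportions, two-sided 0.05, with p̄ the mean of p1 and p2:

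power = Φ{[|p1 − p2| − 1.96·√(2p̄(1 − p̄)/n)] / √([p1(1 − p1) + p2(1 − p2)]/n)}

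For 5% versus 15% at n = 60: 1.96 × √(2 × 0.10 × 0.90/60) = 1.96 × 0.0548 = 0.1074, and √((0.0475 + 0.1275)/60) = 0.0540. Then (0.10 − 0.1074)/0.0540 = −0.136, and Φ(−0.136) = 44.6%.

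| Placebo vs midodrine (assumed) | 60 per arm | 50 per arm |
|---|---|---|
| 5% vs 15% | 44.6% | 38.3% |
| 5% vs 20% | 70.5% | 62.4% |
| 5% vs 25% | 87.6% | 80.9% |
| 5% vs 30% | 95.9% | 92.0% |

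Recording would make reactions at such rates visible and large excesses detectable. Modest excesses would often be missed by a significance test.

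**The case against.** The strongest defence is that this is a deliberate, targeted safety design. The protocol separates effects it regards as uncomfortable from the haemodynamic risks, and it records all of the latter by arm, together with new organ failure, qualifying serious events and ICU readmission. Daily SOFA is collected and a monitoring board reviews the reports. **This stands:** the trial does produce randomised safety evidence.

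Symptom items would also be poorly ascertained. The Subject Protection section expects competency to fluctuate with sedatives or delirium, and a *no* from a patient who cannot report is false reassurance. **This stands** against a plain yes/no for pruritus and paraesthesia. It has less force for urinary retention or a routine liver test.

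Pilomotor reactions could reveal the arm, and the primary endpoint depends on when vasopressors are stopped. **This stands**, and the fix is narrowed for it.

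The rates in Step 3 are assumed, and 5–10% does not suit raised liver enzymes, which the protocol lists as rare. A non-significant comparison at 38–45% power could itself be misread as tolerability. **Both stand** as limits on the size of the point. They favour reporting counts with little weight on tests.

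What does not stand is the unrelated-events rationale as a reason to omit every known drug reaction, or the closing sentence of Adverse Event Reporting as a remedy. If that sentence was meant to widen the scope, it conflicts with the limit above it and needs reconciling.

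**Conclusion.** The point holds in a limited form. The protocol confines recording to a list that excludes, unless serious, all four reactions it calls very common, as well as urinary retention and liver-enzyme rises short of organ failure. The trial can support a haemodynamic safety comparison but not a tolerability profile, and the SAP's adverse-event comparison would understate known midodrine reactions. This rests on the text alone. The size (6 or 3 expected cases in 60 patients) rests on assumed rates of 10% or 5%. It is worth correcting, and it does not affect the primary analysis.

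A reader might infer three stronger things that the documents do not support.
- *That the trial fails a stated safety aim.* The wording "Information gathered from this study will help researchers determine if midodrine is safe and effective" sits under Possible Benefits. The Purpose adds to efficacy only hospital stay and ICU readmission, and the SAP's primary hypothesis concerns vasopressor duration alone.
- *That the trial yields no usable safety evidence.* The named haemodynamic risks and new organ failure are recorded by arm.
- *That the sponsor plans to present unrecorded reactions as absent.* No section says so. The risk is one of interpretation.

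**What to change.** Reconcile Adverse Event Reporting with the daily assessment promised in the risk section:

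1. Add to the pre-specified list dysuria or new urinary retention, and raised liver enzymes where routine results are available. No new tests are needed. State the enzyme threshold in advance, and report how many patients in each arm had a result.
2. Add pruritus or paraesthesia only for patients able to report, with *not assessable* as a category distinct from *no*.
3. Have study staff who do not manage vasopressors record these items at the existing daily assessment.
4. Omit pilomotor reactions, or keep that item from the treating team, to protect blinding.
5. Report counts and denominators by arm, descriptively or under the SAP's existing adverse-event comparison, with a statement that a non-significant difference is not evidence of tolerability.
6. In any case, narrow *safe* under Possible Benefits to the events actually recorded. If items 1–3 are not adopted, also state that tolerability was not assessed.

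The cost is a little more data entry, a staffing constraint on who completes the items, incomplete ascertainment in sedated or delirious patients and on liver enzymes (tested only when care requires), and limited power for modest differences. Item 6 is a wording change only.

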### Outcomes

Study endpoints include the following:

- *Primary endpoint:*
  - Hours from initiation of midodrine until discontinuation of IV vasopressors
- *Secondary endpoints:*
  - ICU length of stay (LOS), hospital LOS, rates of ICU readmission
- *Safety endpoints:*
  - hypertension (increase in blood pressure to a systolic blood pressure (SBP) 20 percent higher than the predefined goal set by the primary team), bradycardia (decrease in heart rate 20 percent lower than the predefined goal set by the primary team), hemodynamically significant tachyarrhythmia (>20 percent decrease in systolic blood pressure).

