### Outcomes

- *Primary endpoint:*
  - Time until discontinuation of IV vasopressors, measured in hours from initiation of midodrine until discontinuation of IV vasopressors
- *Secondary endpoints:*
  - Time to ICU discharge readiness, defined as the number of days from study drug initiation to meeting discharge criteria
  - ICU length of stay, defined as the number of days in the ICU prior to transfer to the general floor
  - Hospital length of stay, defined as the total number of days in the hospital after first study drug administration
  - Rates of ICU readmission, defined as the number of patients readmitted back to the ICU after prior discharge to the general floor
- *Safety endpoints:*
  - Hypertension (increase in blood pressure to a systolic blood pressure (SBP) 20 percent higher than the predefined goal set by the primary team), bradycardia (decrease in heart rate 20 percent lower than the predefined goal set by the primary team), hemodynamically significant tachyarrhythmia (>20 percent decrease in systolic blood pressure).

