### Data Collection

Baseline descriptive data collection will occur on day of enrolment and includes age, sex, ethnicity, APACHE II score, admission diagnosis, pre-existing co-morbidities (diabetes, coronary artery disease, asthma, peripheral vascular disease, renal failure, psychiatric disease, musculoskeletal disease, and others) obtained from the subject, the subject's family, and the subject's medical chart. Baseline laboratory data will be recorded (haemoglobin, white cell count, alanine aminotransferase (ALT), international normalised ratio (INR), bilirubin, urea, creatinine, troponin, lactate). During the study daily SOFA scores, blood pressure goals, total fluid balances, transfused red blood cell units, administered corticosteroids, use of epidural analgesia, vasopressor and study drug start and end

times will be recorded. Days between admission and discharge from the ICU and hospital will be recorded. Readmissions to the ICU during the hospital stay will be identified through daily medical record review.

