#### *Analysis of primary and secondary outcomes*

A parametric t-test or Mann-Whitney U test will be used, as appropriate, to determine whether time from initiation of midodrine until discontinuation of IV vasopressors, time from ICU admission to ICU discharge readiness, and ICU and hospital LOS differ between groups.

A Chi-Square or Fisher's exact test will be used to test whether rates of ICU readmission and incidence of adverse events are different between treatment groups.

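### The plan neither requires all-cause deaths to be recorded nor compares them by arm, and an early death can make hospital stay and ICU readmission look better

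*Combined protocol and SAP*

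**What the plan says.** - **Protocol, Adverse Event Reporting.** Because these patients are critically ill, "we will limit the scope of our AE monitoring and recording to the following". In the list that follows, death enters as "Death, believed to be related to the study drug, or a death that is unexpected considering the acuity of a patient".
- **Protocol, Outcomes.** The secondary endpoints are "ICU length of stay (LOS), hospital LOS, rates of ICU readmission". The safety endpoints are hypertension, bradycardia and tachyarrhythmia. Mortality is in neither list.
- **SAP, Outcomes.** Time to ICU discharge readiness is added, but not mortality. The stay definitions are "ICU length of stay, defined as the number of days in the ICU prior to transfer to the general floor" and "Hospital length of stay, defined as the total number of days in the hospital after first study drug administration". Readmission counts patients who return to the ICU after going to the floor.
- **SAP, Data Collection.** "Days between admission and discharge from the ICU and hospital will be recorded", and charts are reviewed daily for readmissions. Vital status, date of death and discharge disposition are not listed.
- **SAP, Analysis of primary and secondary outcomes.** The durations are compared by t-test or Mann-Whitney U, with no rule for deaths. Under Missing data, patients without an outcome value are left out of that analysis.
- **Protocol, Study Procedures.** Death appears once more, as a reason to stop study drug.

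**The concern.** Judging deaths one at a time does not show an imbalance. Study staff are blinded, and a death that seems in keeping with the patient's illness looks the same in either arm. Only counts by arm can show an excess, and the plan does not call for them.

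The protocol's Purpose section claims less vasopressor time and a shorter ICU stay, with no longer hospital stay and no added risk of readmission. Hospital stay and readmission are thus the guards against harm, and death moves both in the favourable direction. A reader of the results could not tell a shorter stay due to recovery from one due to death, and the claim of benefit without added risk could not be judged.

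**Working it through.** **1. How a death enters each measure under the text as written**

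| Measure | Patient who dies |
|---|---|
| Serious adverse event | Counted only if judged drug-related or unexpected |
| Hospital stay | Ends at death; an early death is a short stay |
| ICU stay | Runs to floor transfer, which a death in the ICU never reaches; no defined value, so it may be dropped as missing |
| ICU readmission | Impossible after a death in the ICU; time at risk is cut short by a death on the floor |
| All-cause mortality | Not an endpoint |

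**2. Precision of a mortality comparison**

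The target of 120 at 1:1 (SAP, Sample size estimation and Randomisation) gives n = 60 per arm. The documents give no mortality, so p = 5% to 15% is assumed, that is 60 × 0.05 = 3 to 60 × 0.15 = 9 deaths per arm. With equal rates, the 95% CI half-width for the risk difference is 1.96 × √(2p(1−p)/60):

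- p = 0.05: 1.96 × √(0.095/60) = 0.078
- p = 0.10: 1.96 × √(0.18/60) = 0.107
- p = 0.15: 1.96 × √(0.255/60) = 0.128

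Power at two-sided 0.05 (normal approximation) is Φ[(|p1−p2| − 1.96√(2p̄(1−p̄)/60)) / √((p1(1−p1)+p2(1−p2))/60)], where p̄ is the mean of the two rates. For 5% vs 10% this is Φ[(0.05 − 1.96 × 0.0481)/0.0479] = Φ(−0.92) = 18%. The same formula gives 45% for 5% vs 15% and 33% for 10% vs 20%.

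**3. Effect on hospital stay**

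This is an illustration, and all its stay and death inputs are assumptions. Hospital stay is lognormal with median 10 days and log-SD 0.8, identical in both arms. Deaths replace the stay with a value uniform on 0.5 to 4 days. There are 60 per arm, 4,000 simulated trials per scenario, and a Mann-Whitney U test at two-sided 0.05. A false benefit is a significantly shorter stay on midodrine; its nominal rate is 2.5%.

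| Deaths, placebo vs midodrine | False benefit, death as short stay | Mean difference in medians, midodrine minus placebo (days) | False benefit, death ranked worst |
|---|---|---|---|
| 5% vs 5% | 3.1% | −0.04 | 2.6% |
| 5% vs 10% | 6.5% | −0.6 | 1.0% |
| 5% vs 15% | 13.8% | −1.1 | 0.3% |
| 5% vs 20% | 25.6% | −1.8 | 0.0% |

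The simulation error on the first figure is √(0.0305 × 0.9695/4000) = 0.27 percentage points, so with equal deaths the rate is close to nominal.

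**The case against.** **Deaths could be recovered.** A reader might infer that the trial cannot compare deaths at all. The documents do not go that far. The adverse event rule limits adverse event recording, not all data capture. A death on study drug is a stopping event, charts are reviewed daily, and the Data Safety Monitoring Board sees the data collected as well as adverse event reports. This stands. But no listed data item asks for vital status, deaths after study drug ends are not covered even as a stopping event, and nothing obliges anyone to give the Board a full count.

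**Many deaths here might qualify as unexpected.** It is tempting to assume that most deaths would be called expected and go unrecorded. The population is selected for low vasopressor rates, with several severe conditions excluded, and is described as nearly fit to leave the ICU. The share of deaths that would meet the rule is unknown. New organ failure is also recorded and could precede some deaths. This stands, and the point does not rest on that share.

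**The bias is modest.** With an assumed 5-point excess and 5 to 7 days lost per death, mean stay falls by 0.05 × 5 = 0.25 to 0.05 × 7 = 0.35 day. If the SD of stay is 5 to 13 days, the standard error of the difference is SD × √(2/60) = 0.9 to 2.4 days, so the shift is about 0.1 to 0.4 standard errors. A reader might set 0.25 day beside the 6 h in the sample size section, but that target concerns time to stopping vasopressors, and the plan sets none for hospital stay. The stay outcomes are also declared exploratory.

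**ICU stay.** A shorter ICU stay through death does not follow from the text. The value is undefined and may be excluded, which distorts the comparison in another way.

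**Low power.** Even with complete capture, a real imbalance would often miss significance. That is a reason to report deaths descriptively, not to leave them uncounted.

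**Conclusion.** The point holds in this form: the plan does not require collection of all-cause deaths, does not compare them by arm, and has no rule for deaths in its stay analyses. The short-stay mechanism applies directly to hospital stay. ICU stay has no defined value for a death in the ICU, and readmission is made impossible by such a death.

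The size depends on death rates that the documents do not give. With equal, low mortality the bias is small. In the illustration, the chance of a falsely shorter hospital stay is about 6.5% with a 5-point excess on midodrine and 14% with a 10-point excess. These rest on the assumed stay distribution and on deaths occurring within the first 4 days. The documents do not support saying that deaths cannot be recovered, that most would go unrecorded, or that the bias rivals the 6 h target.

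This should be corrected. The reason given for limiting adverse event recording, frequent unrelated events in critical illness, does not extend to a count of deaths.

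**What to change.** 1. In SAP Data Collection, add vital status and date of death to hospital discharge for every dosed patient, regardless of attribution.
2. In the Outcomes sections of the protocol and the SAP, add all-cause ICU and in-hospital mortality as safety endpoints. Report counts by arm, the risk difference and an exact 95% CI, to the Data Safety Monitoring Board and in the results.
3. In SAP Analysis of primary and secondary outcomes, pre-specify a sensitivity analysis of hospital and ICU stay with deaths ranked as the worst outcome. It changes what stay measures, so it should accompany the planned analysis and not replace it.
4. Keep the limited scope for all other adverse events.

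**Cost.** Vital status and date of death for each patient, from charts already reviewed daily, and a few lines of SAP text. The mortality comparison will be imprecise, about ±8 to ±13 percentage points at an assumed 5% to 15% mortality, and must be labelled as safety and not efficacy.

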Although frequently prescribed as an off-label indication, the optimal dosing range for midodrine in the treatment of hypotension unrelated to orthostasis has yet to be fully determined. Our proposed study will use the maximum dose that has been previously shown to have a strong correlation with effect on systolic blood pressure. This dosing is based on a recently published randomised, two-centre, double-blind, four-way complete crossover, single dose study in patients with neurogenic orthostatic hypotension. This study demonstrated that there was a linear relationship between dose and change in systolic blood pressure when administering a single dose of midodrine from 2.5 mg to 20 mg. These doses also produced a predictable blood pressure response and blood concentrations. The time to maximum concentration of midodrine was 15 to 30 minutes with an elimination half-life equal to 30 minutes, and active metabolite, dysglymidodrine, equal to 4 hours. There are limited efficacy and safety data supporting off-label use. Based on billing records, a total of 6,443 patients were prescribed midodrine as an inpatient at MGH since 1998. Utilisation of midodrine has steadily increased over the last decade with 1,200 patients being prescribed in 2010. Given that midodrine is only indicated to treat rare diseases, it is likely that the majority of these patients were prescribed midodrine as an off-label indication.

The only information available for off-label treatment of hypotension unrelated to orthostatic dysregulation is based on observational data. Midodrine was successfully used as an alternative to intravenous vasopressors in the treatment of hypotension related to carotid artery stenting. Eleven patients received intravenous dopamine infusion in an intensive care setting whereas 4 patients received midodrine in a regular telemetry floor to treat hypotension. The cost of hospitalisation was significantly higher in the dopamine group due to the need for ICU admission and no major side effects were noted in either group. In another study, midodrine was used as an alternative to intravenous inotropic therapy in patients with hypotension associated with stunned myocardium. The authors concluded that midodrine can shorten the duration of intensive care unit and hospital stay in this setting. At MGH's ICUs,

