### Study Procedures

Prior to randomisation, if subjects are eligible based on inclusion/exclusion criteria, informed consent will be obtained from participants. Once informed consent is obtained, the following information will be collected from the subject's medical record: demographics, past medical/surgical history, preadmission medication list, severity of illness at time of admission, blood pressure, aspartate aminotransferase, alanine aminotransferase creatinine, troponin, cortisol level.

The study drug or placebo will be selected based on the randomisation scheme and prepared by investigational pharmacists. All study personnel will be blinded, except the investigational pharmacist, to the treatment group of the subject. Subjects will be randomised to receive either 20 mg PO every 8 hours of midodrine, or placebo PO every 8 hours.

The study drug will be delivered in a double-blinded manner until:

- ICU discharge
- Rate of phenylephrine exceeds 100 mcg/min, or rate of norepinephrine exceeds 8 mcg/min, or rate of metaraminol exceeds 60mcg/min
- Subject exhibits signs and symptoms of organ failure or hypoperfusion
- Serious allergic adverse event related to midodrine
- Epinephrine requirement
- Death

If the blood pressure goal is met for more than 24 hours without IV vasopressors and the attending physician determines that the study drug is no longer required, the study drug may be discontinued at the discretion of the treating physician.

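### Adverse events are compared over a window that outlasts study drug, with no on-treatment analysis of the three haemodynamic safety endpoints beside it

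*Combined protocol and SAP*

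**What the plan says.** - **Window.** Protocol, Adverse Event Reporting: "Evidence for adverse events related to midodrine will be assessed until completion of all study measurements". No calendar limit and no limit after the last dose is given. The same section expects unrelated events during the hospital stay and restricts which types of event are recorded, but not when.
- **Latest measurements named.** SAP, Outcomes: "Hospital length of stay, defined as the total number of days in the hospital after first study drug administration". SAP, Data Collection: "Readmissions to the ICU during the hospital stay will be identified through daily medical record review".
- **End of dosing.** Protocol, Study Procedures: "The study drug will be delivered in a double-blinded manner until" one of several listed events, the first being ICU discharge. It may end sooner: after more than 24 h at the blood pressure goal without IV vasopressors, "the study drug may be discontinued at the discretion of the treating physician".
- **Persistence of the drug.** Protocol, Significance and Background, gives the parent drug and metabolite "with an elimination half-life equal to 30 minutes, and active metabolite, dysglymidodrine, equal to 4 hours".
- **Test.** SAP, Analysis of primary and secondary outcomes: Chi-square or Fisher's exact test of whether "incidence of adverse events are different between treatment groups".
- **Safety endpoints.** Hypertension, bradycardia and haemodynamically significant tachyarrhythmia are defined in both Outcomes sections without a time window. No on-treatment or exposure-adjusted safety analysis appears anywhere.

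**The concern.** The three safety endpoints are short-acting haemodynamic effects, and the drug is short-acting too. If they are counted through a hospital stay that continues after dosing, events from the drug-free period enter both arms at about the same rate. The planned tests take one yes/no per patient, so a placebo-like event on the ward weighs the same as an event an hour after a dose. A patient who would have had a late event anyway cannot contribute to an on-drug difference.

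This pushes the risk ratio toward 1. In an efficacy comparison that would be conservative; in a safety comparison it is falsely reassuring. The protocol's Possible Benefits section says the trial should inform whether midodrine is safe as well as effective, so the comparison carries weight.

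**Working it through.** The plan states no figure for adverse events, so there is none to reproduce. The sample size of 50 per group (target 120) is set for the primary endpoint; it is used here only as the number of patients available.

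**1. How long the drug persists.** Input: 4 h metabolite half-life (Significance and Background). Fraction remaining = 0.5^(hours/4).
- 20 h: 0.5^5 = 3.1%
- 24 h: 0.5^6 = 1.6%, about 2%

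**2. How late events dilute an on-drug excess.** Let p be the risk while on drug and q the off-drug risk, equal in both arms. Whole-window risk = 1 − (1 − p)(1 − q). The risk difference is multiplied by (1 − q), and the risk ratio moves toward 1.

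Assumed: p = 5% placebo, 20% midodrine; 60 per arm; two-sided 0.05; normal-approximation power.

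| q | placebo | midodrine | RR | power |
|---|---|---|---|---|
| 0 | 5% | 20% | 4.0 | 70.5% |
| 10% | 14.5% | 28% | 1.93 | 43.9% |
| 20% | 24% | 36% | 1.50 | 29.8% |
| 30% | 33.5% | 44% | 1.31 | 21.7% |

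Exact Fisher power is lower but falls in the same way: 62.7%, 35.3%, 23.4%, 16.6%.

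**3. The same question with daily rates, varying the off-drug rate.** Assumed: background 0.05 events/day on drug, tripled to 0.15 by midodrine, 4 days on drug, 50 per arm. Risk = 1 − exp(−sum of rate × days).

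On-drug window only:
- placebo 1 − exp(−0.05 × 4) = 18.1%
- midodrine 1 − exp(−0.15 × 4) = 45.1%
- RR 2.5, power 84%

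Ten-day window, so 6 days off drug:

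| off-drug rate/day | placebo | midodrine | RR | power |
|---|---|---|---|---|
| 0 | 18.1% | 45.1% | 2.5 | 84% |
| 0.005 | 20.5% | 46.7% | 2.3 | 80% |
| 0.01 | 22.9% | 48.3% | 2.1 | 76% |
| 0.05 | 39.3% | 59.3% | 1.5 | 52% |

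With a 15-day window and 0.05/day off drug: 52.8% against 68.3%, RR 1.3, power 36%.

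**4. Do the windows differ by arm?** With the same assumed rate of 0.05/day in both arms and a 10-day window on placebo, the spurious difference 1 − exp(−0.05 × 10) minus 1 − exp(−0.05 × T) is:
- T = 10 days: 0
- T = 9.75 days (6 h shorter): 0.8 points
- T = 9 days: 3.1 points
- T = 8 days: 6.4 points

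If the window runs to hospital discharge, T changes only if hospital stay or survival changes. The Purpose section hypothesises a shorter ICU stay but only no increase in hospital stay; Possible Benefits lists a shorter hospital stay as a possibility.

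**The case against.** The case on the other side has five parts.

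- **The window is inferred.** Hospital discharge is not named as the end of assessment, and ever/never counting is deduced from the choice of test. This stands. It narrows the claim, but an undefined end is itself something the SAP should settle.
- **Late events may not be counted.** The sentence is limited to events related to midodrine, and hypertension and bradycardia are judged against goals set by the primary team, which the documents do not say are kept after the ICU. This stands as a reason why dilution could be nil. No attribution rule is given, however, so the plan does not guarantee it.
- **Late events are not always irrelevant.** The half-life comes from a single-dose study in neurogenic orthostatic hypotension, and new organ failure, death or disability can emerge after washout. This stands: it would be too strong to say that late events cannot be drug effects, and the whole-stay comparison should stay.
- **An on-treatment window has its own bias.** Drug stops for vasopressor escalation, organ failure, epinephrine or at physician discretion, all after randomisation and possibly related to treatment. A rate per patient-day corrects for length, not for informative stopping. This stands, and is why the on-treatment analysis belongs beside the whole-stay comparison and does not replace it.
- **Unequal windows.** A reader might infer that a shorter stay on midodrine shortens its observation window and so hides harm. The documents do not support that as a general claim: a shorter ICU stay leaves a to-discharge window unchanged. For example, 3 days on drug against 4 hides a one-third higher daily rate completely if only drug time is counted (1 − exp(−0.05 × 4/3 × 3) = 1 − exp(−0.05 × 4) = 18.1%). With both arms followed for 10 days at 0.05/day off drug, the same inputs give 42.3% against 39.3%.

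**Conclusion.** The concern holds in a limited form. Adverse-event assessment continues past the end of dosing to an undefined point, the planned tests ignore time on drug, and nothing in the SAP isolates the period in which a haemodynamic drug effect is plausible. Any late hypertension, bradycardia or tachyarrhythmia that is counted moves the comparison toward no difference.

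The size cannot be fixed from the documents. In the daily-rate illustration, 10-day power at 50 per arm lies between 52% and 84%, depending only on the off-drug event rate; with few or no late events recorded, nothing is lost. A reader might conclude that the plan is shown to bias the safety result toward reassurance. The documents support only that it leaves this possible and provides no analysis that would reveal it. A between-arm difference in window length requires an effect on hospital stay or mortality, and a 6 h difference alone is worth under 1 percentage point at the assumed rates.

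**What to change.** In the SAP sections Outcomes and Analysis of primary and secondary outcomes:

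- State when adverse-event assessment ends.
- Keep the whole-stay incidence comparison for all adverse events, including new organ failure and serious events.
- Pre-specify beside it an on-treatment analysis of hypertension, bradycardia and haemodynamically significant tachyarrhythmia, from first dose to 24 h after last dose (six half-lives of 4 h). Report per arm the patients with an event, the event count and the patient-days, and give the rate ratio with a 95% CI.
- Say that this analysis is to be read with possibly informative stopping of study drug in mind.

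Study drug start and end times are already on the SAP's Data Collection list; a date and time for each event would need to be recorded if it is not already. The cost is some SAP wording, that one data item and one extra table. The on-treatment window will contain fewer events, so its interval may be wide. Treatment, enrolment and the primary analysis do not change.
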